Patients will also be evaluated for other unexpected toxicities according to the NCI CTCAE, Version 3.0. Unexpected Grade 3 toxicities thought to be due to therapy will be scored as 1 and unexpected Grade 4 toxicities thought to be due to therapy will be scored as 2. A patient with both unexpected Grade 3 and Grade 4 toxicities will be counted as a patient with unexpected Grade 4 toxicity. If the total score exceeds 3 in the first 3, 4, or 5 patients, or exceeds 4 at any point within a dose level, enrollment to that dose level will be halted and that dose will be considered beyond tolerance. See Table 4. If this happens at dose level 1, subsequent patients eligible for full dose therapy will enroll into dose level -1. If dose level -1 is found intolerable in patients eligible for full dose therapy, the trial will be stopped.

Table 3:

# of patients with a DLT	Total # patients in cohort	Action
≥3	3, 4, 5	Stop dose-cohort ¹
≥4	6, 7, 8, 9, 10	Stop dose-cohort ¹

¹If this occurs within Dose level 1, enter the next group of patients eligible for full dose to Dose level -1. If dose level -1 is found intolerable in patients eligible for full dose therapy, the trial will be stopped.

Table 4:

# of patients with unexpected Grade 3 ¹	# of patients with unexpected Grade 4	Total # patients in cohort	Action
≥0	≥2	3, 4, 5	Stop dose-cohort ²
≥4	≥0		
≥0	≥3	6, 7, 8, 9, 10	Stop dose-cohort ²
≥1	≥2		
≥5	≥0		

¹A patient with both unexpected Grade 3 and Grade 4 toxicities is counted as a patient with unexpected Grade 4 toxicity

²If this occurs within Dose level 1, enter the next group of patients eligible for full dose to Dose level -1. If patients eligible for full dose cannot tolerate dose level -1, the trial will be stopped.

The development of any Gr. 5 toxicity thought related to therapy will result in temporary suspension of the trial for full evaluation. If specific toxicity related to an irradiated organ is found, alteration of the dose parameters for that tissue will be modified, although not necessarily a reduction in the planned tumor dose.

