2). The secondary study end-point will be local tumor response and control. Our expectation is that a dose of 1500 cGy per fraction for 3 fractions (4500 cGy total) will be adequate for control of irradiated lesions of moderate size, but higher doses may be needed. In the second cohort the optimal dose is less clear, and dose escalation will likely be desired. Patients will be evaluated for local control at 5-6 months after irradiation. A minimum of 10 patients will be entered onto each dose cohort. However, if there are 4 local failures within a cohort at dose level 1 dose escalation may proceed provided the tolerance parameters are acceptable (that is, conditions in both Tables 5A and 5B are satisfied), and patients have been evaluated for toxicity for at least 3 months from the initiation of therapy. At that point, dose escalation to a nominal prescription dose per fraction of 1750 cGy in the first cohort, and 850 cGy in the second cohort, will be undertaken. A second dose escalation with the same increase in dose/fraction could occur based on the same parameters as above. Escalation of the two cohorts will be done separately as their tolerance might be different. No intra-patient dose escalation will be allowed. For dose escalation, if the proposed dose for escalation is found to be too toxic, based on Tables 3 and 4, the study will be stopped. All patients in a cohort will be followed for 3 months from the time of initiation of therapy for evaluation of toxicity, prior to dose escalation in each cohort.

Table 5A

# of patients with a DLT	Total # patients in cohort	Action
0	5, 6, 7, 8	DLT rate warrants escalation to next dose level for subsequent patients ¹
≤ 1	9, 10	DLT rate warrants escalation to next dose level for subsequent patients ¹

¹ Dose escalation will only occur in patients eligible for full dose, see text of protocol

Table 5B

# of patients with unexpected Grade 3 ¹	# of patients with unexpected Grade 4	Total # patients in cohort	Action
≤ 1	0	5, 6, 7, 8	Rate of unexpected toxicities warrants escalation
≤ 2	0	9, 10	Rate of unexpected toxicities warrants escalation
≤ 0	1		

¹ A patient with both unexpected Grade 3 and Grade 4 toxicities is counted as a patient with unexpected Grade 4 toxicity

To summarize, the goal is to find a dose such that:

- 1). The rate of dose limiting hepatic toxicity at that dose does not exceed 0.33.
- 2). The rate of unexpected Grade 3 plus double the rate of Grade 4 toxicities does not exceed 0.4.;

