6.4 Data and Safety Monitoring Plan

The Principle Investigator will provide continuous monitoring of patient safety in this trial with periodic reporting to the Data and Safety Monitoring Committee (DSMC).

As this will be a multi-center study, the following approach will be used to ensure proper data and safety monitoring:

Bi-weekly teleconferences will be held provided patient accrual warrants this schedule, which will include the principal investigators from the participating site (or a designated co-investigator if a PI is unavailable), as well as protocol nurses, clinical research associates, regulatory associates, data managers, biostatisticians, and any other relevant personnel the principal investigators may deem appropriate. Subject accrual, toxicity assessments, dose modification, protocol adherence, data entry, validity, integrity, and completeness, and management issues will be discussed at the meetings.

The team will produce summaries or minutes of these meetings.. These summaries will be available for inspection when requested by any of the regulatory bodies charged with the safety of human subjects and the integrity of data including, but not limited to, the oversight (Office of Human Research Ethics (OHRE) Biomedical IRB, the Oncology Protocol Review Committee (PRC) or the North Carolina TraCS Institute Data and Safety Monitoring Board (DSMB).

The UNC LCCC Data and Safety Monitoring Committee (DSMC) will review the study on a semi-annual basis. The UNC PI will be responsible for submitting the following information for review: 1) accrual data including the number of patients treated; 2) significant developments reported in the literature that may affect the safety of participants or the ethics of the study; 3) preliminary response data; and 4) summaries of team meetings that have occurred since the last report. Findings of the DSMC review will be disseminated by memo to the UNC PI, PRC, and the UNC IRB and DSMB.

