7.0 DATA MANAGEMENT AND STATISTICAL ANALYSIS

7.1 Study Design

The primary end-point of this study will be hepatic tolerance to the radiation treatment. This will be complicated by patients who could have progressive disease in the liver that could result in worsening liver function studies. Damage secondary to radiation therapy should appear within 3 months, so that will be the primary time for evaluation. Liver tolerance will be determined by the following:

1). The primary end-point will be the development of radiation induced liver disease as measured by the > 2-fold worsening of liver functional parameters, clinically apparent worsening of portal hypertension, new or worsening bleeding esophageal varices, or worsening ascites within the first 3 months from initiation of treatment. These will be considered dose-limiting hepatic toxicities. Increase in hepatic enzymes by less than 2-fold alone will not be considered a dose-limiting radiation induced toxicity if they are not accompanied by other signs of deteriorating liver function as any irradiation of normal liver would be expected to elevate enzymes.. The two patient cohorts will be evaluated separately for determination of toxicity. Deteriorating liver function that can be explained by tumor progression or other non-treatment related events will not be considered a treatment toxicity for the purpose of this analysis.

A dose level will be considered beyond tolerance depending on the fraction of patients who experience a dose-limiting radiation induced hepatic toxicity. See Table 3. Once this happens, enrollment to that dose level will be halted. If this happens at dose level 1, subsequent patients eligible for full dose therapy will enroll into dose level -1. If dose level -1 is found intolerable in patients eligible for full dose therapy, the trial will be stopped.

Patients will also be evaluated for other unexpected toxicities according to the NCI CTCAE, Version 3.0.. Unexpected Grade 3 toxicities thought to be due to therapy will be scored as 1 and unexpected Grade 4 toxicities thought to be due to therapy will be scored as 2. A patient with both unexpected Grade 3 and Grade 4 toxicities will be counted as a patient with unexpected Grade 4 toxicity. If the total score exceeds 3 in the first 3, 4, or 5 patients, or exceeds 4 at any point within a dose level, enrollment to that dose-level will be halted and that dose will be considered beyond tolerance. See Table 4.

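### The unexpected-toxicity limit of 3 is written only from three patients, so two unexpected Grade 4 patients in the first two trigger no written stop, although no result in a third could keep the level open

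*Combined protocol and SAP*

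**What the plan says.** Section 3.2 scores each patient for unexpected toxicity attributed to therapy: Grade 3 counts 1 and Grade 4 counts 2. No patient is counted twice: "A patient with both unexpected Grade 3 and Grade 4 toxicities will be counted as a patient with unexpected Grade 4 toxicity". The stopping condition is "If the total score exceeds 3 in the first 3, 4, or 5 patients, or exceeds 4 at any point within a dose level", and its consequence is that "enrollment to that dose level will be halted and that dose will be considered beyond tolerance". Section 7.1 repeats the rule, including the second limit: "or exceeds 4 at any point within a dose level, enrollment to that dose-level will be halted".

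Table 4 sets out the stopping patterns in two groups by number of patients: 3 to 5 and 6 to 10. In the first group, two or more patients with Grade 4 stop the level. No row covers one or two patients.

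The design goal for these toxicities, at the end of Section 3.2, is: "The rate of unexpected Grade 3 plus double the rate of Grade 4 toxicities does not exceed 0.4".

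Three other provisions bear on the point. Sections 3.2 and 7.2 plan for 10 patients at each level. Section 8.6 requires the study to be run as approved except in an emergency. Section 6.4 says that the principal investigator "will provide continuous monitoring of patient safety in this trial".

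**The concern.** A cumulative score cannot fall as patients are added, so a limit for the first few patients is normally read from the first patient. Here the lower limit is tied to totals of three to five, and the limit with no restriction on patient number is one point higher. Two patients with unexpected Grade 4 toxicity land exactly between the two.

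What is at stake is how the next patient is handled. Under Section 3.2, closing dose level 1 sends later full-dose patients to level -1, closing level -1 stops the trial, and closing an escalated level stops the study. The reading chosen at two patients therefore decides which dose the third patient is assigned, or whether that patient is entered at all. In a multi-center study this should not depend on interpretation, least of all when the third patient adds nothing to the stopping decision.

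**Working it through.** **Inputs.** Weights of 1 (Grade 3) and 2 (Grade 4), one count per patient; limits of more than 3 for three to five patients and more than 4 at any number (Sections 3.2 and 7.1); the Table 4 rows; the weighted-rate goal of 0.4 (Section 3.2). The protocol gives no expected Grade 4 rate, so the rates below are assumptions. Patients are taken as independent with a common rate, and the score is read after each patient.

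**Step 1: reproduce Table 4's first row.** Two Grade 4 patients score 2 × 2 = 4, which exceeds 3. The row for two or more Grade 4 patients at totals of 3 to 5 agrees with the text.

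**Step 2: two patients.** The maximum score is 2 × 2 = 4. The possible patterns are:

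| Grade 3 patients | Grade 4 patients | Score | Above 3? | Above 4? |
|---|---|---|---|---|
| 0 | 0 | 0 | no | no |
| 1 | 0 | 1 | no | no |
| 2 | 0 | 2 | no | no |
| 0 | 1 | 2 | no | no |
| 1 | 1 | 3 | no | no |
| 0 | 2 | 4 | yes | no |

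Only the last row is affected. After one patient the maximum score is 2, so nothing arises there.

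**Step 3: add a third patient to that row.** No event gives 4, Grade 3 gives 4 + 1 = 5, and Grade 4 gives 4 + 2 = 6. All three exceed 3 at a total of three patients, and all three meet Table 4's first row. The decision is already fixed.

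**Step 4: probability.** With Grade 4 rate p, both of the first two patients have Grade 4 with probability p².

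- p = 0.10: 0.01
- p = 0.20: 0.04
- p = 0.30: 0.09

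The protocol's goal requires the Grade 3 rate plus 2p to be at most 0.4. With no Grade 3 toxicity this gives p ≤ 0.20, so 4% is the figure at the ceiling. If the ceiling is reached with 20% Grade 3 and 10% Grade 4 (0.20 + 2 × 0.10 = 0.40), the figure is 1%. A rate of 30% implies a weighted rate of at least 0.6, which is above the goal.

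**Step 5: effect on the stopping probability, p = 0.20, no Grade 3.** The level stops with at least 2 Grade 4 patients in the first 5, or at least 3 in 10.

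- At least 2 of the first 5: 1 − 0.8⁵ − 5 × 0.2 × 0.8⁴ = 1 − 0.32768 − 0.4096 = 0.26272.
- None in the first 5, then at least 3 of the next 5: 0.32768 × 0.05792 = 0.01898.
- One in the first 5, then at least 2 of the next 5: 0.4096 × 0.26272 = 0.10761.
- Sum: 0.26272 + 0.01898 + 0.10761 = 0.3893.

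Starting at two patients instead of three moves only paths that stop anyway, so 0.3893 is unchanged. Expected entries fall by 1 × p² = 0.04, from 8.257 to 8.217. At p = 0.30 the stopping probability is 0.6691 either way, and expected entries fall from 6.823 to 6.733.

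**Step 6: timing.** Section 7.2 expects 40 to 60 patients in 3 years, which is 40/36 = 1.1 to 60/36 = 1.7 per month. Split equally between the cohorts (an assumption), that is about 1.7 to 2.5 entries per cohort in any 3 months. Three months is also the toxicity follow-up required before escalation, and Section 3.2 sets no staggered entry. A third patient may therefore often be enrolled before the second event is known.

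**The case against.** A reader might infer that a third patient must be entered before the level can close. The documents do not support that. No section requires entry to continue to three or forbids earlier closure. The sentence can even be read as already satisfied, because the total for the first three patients is certain to exceed 3. Section 6.4 also provides continuous monitoring by the investigator, regular team calls when accrual warrants them, and semi-annual committee review. Nothing bars a pause after two related Grade 4 events. All of this stands, and it limits the point to a gap in the written trigger.

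It does not close the gap. Section 6.4 attaches no enrollment rule to this state, and the only suspension stated without regard to patient number is for related Grade 5 toxicity. Entry toward 10 patients remains the default, so the text supports two answers.

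A reader might also multiply the effect over at least two levels in each cohort, or count one patient saved each time. Section 7.2 says only that an escalation might be needed in the first cohort and is likely in the second, where it may not be feasible. The assured minimum is one level per cohort. One patient per occurrence is an upper bound, for the timing reason in step 6.

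Finally, text and Table 4 agree in starting at three patients, so on this point there is no contradiction, only an omission.

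**Conclusion.** The point holds as a small wording gap. With two unexpected Grade 4 toxicities in the first two patients, the sponsor's own early limit has been passed but no written trigger halts entry, and the third patient cannot alter the outcome. The size is at most one patient per level, with probability 1% to 4% for assumed Grade 4 rates of 10% to 20%. The chance of stopping the level is unaffected.

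This rests on the attribution of both events to therapy standing, on both being known before the third patient is entered, and on the score being read after each patient. Table 3 has no such gap, because three dose-limiting toxicities cannot occur before three patients. The change is a free improvement rather than a correction of an error in the design.

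**What to change.** Keep the stated threshold. In Sections 3.2 and 7.1, word the first limit as: *exceeds 3 at any point within the first 5 patients*. Label the first patient-number group of Table 4 *5 or fewer*. This adds exactly one stopping state, two Grade 4 patients out of two. The cost is one phrase in two sections and one table label; no threshold or dose changes.

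Relabelling does not settle a separate mismatch in the same table. As its rows read, Table 4 omits some patterns on which the text score stops, for example two Grade 3 patients and one Grade 4 patient (1 + 1 + 2 = 4) at totals of 3 to 5, and three Grade 3 patients and one Grade 4 patient (1 + 1 + 1 + 2 = 5) at totals of 4 to 10. Text and table should be reconciled in the same edit.

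### Table 4 omits stopping combinations with one unexpected Grade 4 patient and several Grade 3 patients that the score rule in Sections 3.2 and 7.1 requires

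*Combined protocol and SAP*

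**What the plan says.** Section 3.2 sets up a score for unexpected, treatment-related toxicity: "Unexpected Grade 3 toxicities thought to be due to therapy will be scored as 1", while a Grade 4 counts double, for 2 points. Each patient contributes once, at the higher grade: "A patient with both unexpected Grade 3 and Grade 4 toxicities will be counted as a patient with unexpected Grade 4 toxicity". The dose level is halted and declared beyond tolerance "If the total score exceeds 3 in the first 3, 4, or 5 patients, or exceeds 4 at any point within a dose level". Section 7.1 repeats the rule in the same terms. Both sections then point to Table 4.

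Table 4 in Section 3.2 lists these stopping combinations:

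- 3, 4 or 5 patients: at least 2 Grade 4; or at least 4 Grade 3.
- 6 to 10 patients: at least 3 Grade 4; or at least 1 Grade 3 with at least 2 Grade 4; or at least 5 Grade 3.

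Its footnote gives the consequence at dose level 1: later patients eligible for full dose go to level -1, and the trial stops if level -1 is not tolerated either. For escalated doses, Section 3.2 names the tables as the standard: "if the proposed dose for escalation is found to be too toxic, based on Tables 3 and 4, the study will be stopped". The stated target for this type of toxicity is "The rate of unexpected Grade 3 plus double the rate of Grade 4 toxicities does not exceed 0.4".

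**The concern.** A stopping rule given both as a sentence and as a table should give one answer for any set of data. Table 4 handles Grade 3 patients alone, and two or more Grade 4 patients, but no row addresses exactly one Grade 4 patient together with Grade 3 patients. Some of those combinations score high enough to stop under the sentence.

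Where the two disagree, the text calls the dose beyond tolerance and the table does not. At dose level 1 this decides whether later full-dose patients move down to level -1. At an escalated level it decides whether the study stops. It also decides how the dose is labelled, and finding a tolerable dose is the primary objective (Section 2.1). Someone working from the table alone would go on filling the planned 10 places at that level.

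**Working it through.** **Inputs.** Let *a* be the number of patients counted as Grade 3, *b* the number counted as Grade 4, and *n* the number treated at the dose level, with a + b ≤ n. All rules come from Section 3.2; the score rule is repeated in Section 7.1.

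- Score: S = a + 2b.
- Text rule: stop if S > 3 at n = 3 to 5, or S > 4 at any n.
- Table 4: stop at n = 3 to 5 if b ≥ 2 or a ≥ 4; stop at n = 6 to 10 if b ≥ 3, or (a ≥ 1 and b ≥ 2), or a ≥ 5.

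**Step 1: do the rows that exist agree with the score?** Yes. At n = 3 to 5, two Grade 4 give 2 × 2 = 4 > 3, and four Grade 3 give 4 > 3. At n = 6 to 10, three Grade 4 give 6 > 4, one Grade 3 with two Grade 4 gives 1 + 4 = 5 > 4, and five Grade 3 give 5 > 4. Two Grade 4 alone give 4, which does not exceed 4, so leaving that out of the second block is right.

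**Step 2: which combinations are missing?** For each n there are (n + 1)(n + 2)/2 pairs (a, b). For n = 3 to 10 that is 10 + 15 + 21 + 28 + 36 + 45 + 55 + 66 = 276. Comparing the two rules in every one gives these outcomes where the text stops and Table 4 has no row:

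| Grade 3 patients | Grade 4 patients | Score | n | Outcomes |
|---|---|---|---|---|
| 2 | 1 | 4 | 3, 4, 5 | 3 |
| 3 | 1 | 5 | 4 to 10 | 7 |
| 4 | 1 | 6 | 6 to 10 | 5 |

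The total is 3 + 7 + 5 = 15. All have exactly one Grade 4 patient. There is no outcome where the table stops and the text does not. At n = 1 or 2 the score cannot exceed 4, so nothing is lost by the table starting at 3.

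The table also treats equal scores differently. At n = 5 it stops four Grade 3 (score 4) but not two Grade 3 with one Grade 4 (score 4). At n = 6 to 10 it stops one Grade 3 with two Grade 4 (score 5) but not three Grade 3 with one Grade 4 (score 5).

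**Step 3: could escalation follow from a missed outcome?** No. Table 5B requires no Grade 4 patient at n = 5 to 8, and at n = 9 or 10 allows one only with no Grade 3 patient. None of the 15 qualifies.

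**Step 4: how often would it matter?** The documents give no expected rates, so these are assumptions. The probabilities come from an exact patient-by-patient calculation up to 10 patients, with both rules checked after each patient from the third. It assumes each patient is assessed before the next enrols and leaves out the hepatic DLT rule in Table 3. The score rate is the Grade 3 rate plus twice the Grade 4 rate, to be compared with the 0.4 target.

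| Grade 3 / Grade 4 rate | Score rate | Stop, text | Stop, Table 4 | Gap (points) | Extra patients under the table |
|---|---|---|---|---|---|
| 5% / 5% | 0.15 | 5.3% | 4.9% | 0.5 | 0.02 |
| 10% / 5% | 0.20 | 8.8% | 6.4% | 2.3 | 0.08 |
| 20% / 5% | 0.30 | 20.2% | 11.1% | 9.1 | 0.28 |
| 20% / 10% | 0.40 | 39.7% | 27.5% | 12.2 | 0.45 |
| 30% / 5% | 0.40 | 38.2% | 23.2% | 15.0 | 0.54 |
| 30% / 10% | 0.50 | 58.3% | 39.2% | 19.1 | 0.85 |
| 40% / 10% | 0.60 | 76.2% | 57.6% | 18.6 | 1.15 |

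Gaps are taken before rounding.

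**The case against.** The strongest reply is that the correct rule is already in the protocol, stated twice in operative terms, and applies at any point within a dose level, escalated levels included. The Amendment 1 summary describes Tables 3 and 4 as added to underline the definitions, and Table 4 is silent in the missing cells; it does not say to continue. Section 7.1 restates the score rule without the sentence that ties escalated doses to the tables. On that reading the text governs and nobody is misled.

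This lowers the chance of harm but does not settle which rule applies. Nothing in the protocol says the sentence prevails over the table. Table 4 has its own action column and footnoted consequences, and for escalated doses Section 3.2 names Tables 3 and 4 without the score.

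The remaining objections concern size, and they stand. Table 5B blocks escalation. Table 3 runs alongside, and a related Grade 5 event suspends the trial. The team calls in Section 6.4 include biostatisticians and could catch a case. The larger gaps need high rates of unexpected toxicity, whereas Section 7.2 expects the starting parameters to be safe; at 5% Grade 3 and 2% Grade 4 the stopping probabilities are 1.08% and 0.84%. At a score rate of 0.4 the dose still meets the target, so the gap there is not lost protection. Enrolment may also overlap, so the extra-patient figures are not forecasts. A table row lost when the PDF was read cannot be fully excluded, though both blocks look intact.

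**Conclusion.** The concern holds. Table 4 and the score rule disagree in 15 of 276 outcomes, always with the table as the less strict of the two. That count is exact and needs no assumption about toxicity rates.

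The practical size does depend on assumed rates. The table alone stops about 0.5 to 2 percentage points less often at the low rates tabulated, and about 19 points less often at the two settings above the protocol's 0.4 limit. Expected extra enrolment is between 0.02 and 1.15 patients per dose level. The consequence is further treatment at, and a wrong tolerability label for, a dose the text has declared beyond tolerance; it is not escalation past that dose. Because this is a safety threshold feeding the primary objective, it should be corrected even though the expected number of patients affected is small.

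**What to change.** Add two stop rows to Table 4:

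- for 3, 4 or 5 patients: at least 2 Grade 3 with at least 1 Grade 4;
- for 6 to 10 patients: at least 3 Grade 3 with at least 1 Grade 4.

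Leave the score sentence in Sections 3.2 and 7.1 as it is. Repeating the enumeration with these rows gives no disagreement in any of the 276 outcomes, and the stopping probabilities become those in the text column above. The reference to Tables 3 and 4 for escalated doses then needs no change. The cost is two table rows in an amendment, with no added data, patients or follow-up.
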